# 5.8.4.2 Change from Baseline in Total Cholesterol, LDL, HDL, and Triglycerides after 13 Weeks of treatment

Post-baseline Last observation carried forward (LOCF) approach will be used to impute missing value at Week 13. Only assessments for subjects who are on treatment for more than 28 days, collected on or before treatment discontinuation + 3 days will be used for LOCF. The change from baseline in total cholesterol, LDL and HDL will be analyzed using ANCOVA model with change from baseline at Week 13 as the response variable, treatment, gender, baseline value as covariates.

Triglycerides is not expected to be normally distributed. The Hodge-Lehmann method will be used to estimate the median difference with 90% CI between treatment groups. A Wilcoxon rank sum test will be performed.

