**Table 2: Study Schedule of Assessments (Continued)**

SOA													
	Screening Period	Treatment Phase by Week											ET or Post Study F/U
Visit Number	1	2 Rand.	3	4	5	6	7 g	8	9	10	11 g	12	13
Week e	~4 Weeks	Week 0	Week 1	Week 2	Week 3	Week 4	Week 5	Week 6	Week 8	Week 10	Week 12	EoT 13	Week 15
Study Day	-28	1	8	15	22	29	36	43	57	71	85	92	105
Visit Window (days)	0	0	±2	±2	±2	±2	±3	±3	±3	±3	±3	±3	±3
Heart Rate/Blood Pressure	X	X	X	X	X	X		X	X	X		X	X
Respiratory Rate/Temperature	X	X											X
Triplicate 12-lead ECG	X	X						X				X	
PHQ-9	X												
Laboratory and Safety Assessments													
General Safety Labs: Chemistry b, c	X	X				X			X			X	X
Fasting lipid Panel		X										X	
General Safety Labs: Hematology	X	X						X				X	X
Liver Function Test			X	X	X			X		X			
Urine Drug Screen	X												

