### **8.3. Subject Withdrawal Criteria**

#### **8.3.1. Procedures for Discontinuation or Withdrawal of a Subject**

##### **8.3.1.1. Discontinuation of Trial Treatment**

Discontinuation of trial product can be decided by either the investigator or the subject. A participant may discontinue his or her participation without giving a reason at any time during the trial.

Participants who discontinue trial product should continue with the scheduled visits and assessments to ensure continued counselling and data collection.

If the subject does not wish to attend the scheduled clinic visits, efforts should be made to have the visits converted to phone contacts. However, all efforts should be made to have the subject attend at least the 'end of treatment' clinic visit containing the final data collection of primary and confirmatory secondary efficacy endpoints, and the 'end of trial' visit.

The 'end of trial' visit is scheduled approximately 2 weeks after the final data collection, to ensure the safety of the subject. If the subject has discontinued trial product >2 weeks prior to the 'end of treatment' visit, and the requirements for the follow-up period prior to the 'end of trial' visit is fulfilled, then the 'end of trial' visit can be performed in combination with 'end of treatment' visit.

If the subject refuses to attend the 'end of treatment' and/or 'end of trial' visit, information about the attempts to follow up with the subject must be documented in the subject's medical record.

The subject must be discontinued from trial product if any of the following applies:

1. Safety concern as judged by the investigator
2. Pregnancy
3. Intention of becoming pregnant
4. Liver function test (LFT) abnormalities meeting specified discontinuation criteria (refer to [Appendix A](#) for discontinuation criteria and instruction on management of LFT abnormalities)
5. Confirmed pancreatitis (see below)

If acute pancreatitis is suspected based on clinical signs and symptoms, blinded study medication should be interrupted immediately, and appropriate diagnostic assessments should be performed.

- A diagnosis of acute pancreatitis requires at least 2 of the following 3 findings :
  - abdominal pain consistent with acute pancreatitis (persistent, severe epigastric pain, frequently radiating to the back); abdominal pain is often associated with nausea and vomiting.
  - serum lipase and/or amylase activity  $\geq 3X$  the laboratory ULN

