#### 15.1.5.2. Blood Chemistry

Blood chemistry testing includes the following assessments:

Alanine aminotransferase (ALT)	Phosphorus
Albumin	Potassium
Alkaline phosphatase (ALP)	Sodium
Aspartate aminotransferase (AST)	Total bilirubin
Bicarbonate	Direct bilirubin
Chloride	Total Protein
Cholesterol (full lipid panel on Day 1 and EoT only)	Triglycerides
Creatinine	Urea
Calcium	Gamma-glutamyl transferase (GGT)
Glucose	Magnesium
TSH (Screening)	Multiple biochemical analysis (MBA) a
	Amylase
	Lipase

a MBA testing will include, in addition to above tests: estimated glomerular filtration rate (eGFR) measured by MDRD at screening.

Please refer to Section 8.3 for subject discontinuation criteria related to abnormal liver test results, and Appendix A for details on management and follow-up of LFT elevations.

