### **16.6.2. Secondary Endpoints**

The confirmatory secondary continuous endpoints will be analyzed to address the primary estimand using the same MMRM described for the primary endpoint.

For the secondary categorical endpoint of proportion of subject achieving  $\geq 5\%$  weight reduction after 13 weeks, the same MMRM described for the primary endpoints will be used to address the primary estimand. The missing data will be imputed using MMRM assuming missing at random

(MAR) and the imputed value will be used to classify each subject as a responder or not. A logistical regression using gender and treatment as factors and baseline body weight as covariate will be applied to analyze the imputed data.

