### **16.6.3. Exploratory Endpoints**

The exploratory endpoints will be analyzed using the same approach described for the secondary endpoint.

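### SAP 5.8.4.2 imputes missing Week 13 lipids by LOCF where the protocol specifies the on-treatment MMRM, and SAP Section 8 declares no change

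*SAP*

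**What the plan says.** **Protocol.** Section 16.6.3: "The exploratory endpoints will be analyzed using the same approach described for the secondary endpoint". Section 16.6.2 analyses continuous secondary endpoints "using the same MMRM described for the primary endpoint". Section 16.6.1 gives that model a hypothetical estimand (the effect if everyone had stayed on the assigned treatment to the end) and restricts it to on-treatment assessments.

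**SAP.** Section 5.8.4.2: "Post-baseline Last observation carried forward (LOCF) approach will be used to impute missing value at Week 13". Two limits follow: "Only assessments for subjects who are on treatment for more than 28 days", and then "collected on or before treatment discontinuation + 3 days will be used for LOCF". Total cholesterol, LDL and HDL go into an ANCOVA with treatment, gender and baseline value. Triglycerides get a Hodges-Lehmann estimate and a Wilcoxon rank sum test. The other exploratory family, hemodynamics, keeps the MMRM (SAP 5.8.4.1). SAP Section 8 declares that nothing planned in the protocol was changed.

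**Sampling.** The chemistry list in protocol 15.1.5.2 has "Cholesterol (full lipid panel on Day 1 and EoT only"), with triglycerides as a separate entry. In Table 2, the row "Fasting lipid Panel" is marked only at Visits 2 and 12. The chemistry row is marked on treatment at Visits 6, 9 and 12 (Days 29, 57 and 92).

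**The concern.** There are two problems. The first is documentary: the SAP changes the lipid method, gives no reason, and states that there was no change. Protocol 16.1 requires changes in the planned analyses to be reported in the clinical study report, and an incorrect statement in Section 8 makes that easy to miss.

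The second is the method. LOCF assumes that a participant's value stays where it was at the last draw. The protocol's estimand asks what the Week 13 value would have been with continued treatment. An MMRM under missing at random uses an early draw as an early draw. LOCF relabels it as a Week 13 result and then gives it the same weight as a measured one, so the uncertainty of the imputation is ignored. Because the analytes have different draw schedules, one stated rule also yields different imputed participants and different times on drug for lipids reported side by side.

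**Working it through.** The lipid section states no numerical figure to reproduce. The check sets the rules against the schedule and counts days.

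**1. Which method does the protocol require?** Section 16.6.3 points to 16.6.2, which points to the MMRM in 16.6.1. SAP 5.8.4.2 uses LOCF with a single-visit analysis. The two differ, and SAP Section 8 does not list the difference.

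**2. What can be carried for LDL and HDL?** Scheduled panels fall on Day 1 and Day 92, so there are 0 scheduled post-baseline panels before end of treatment. The rule can act only on an end-of-treatment panel taken early (within 3 days of stopping, after more than 28 days on drug) or on an unscheduled panel.

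**3. What can be carried for triglycerides?** Dosing runs from Day 1 to Day 91, and the maintenance dose of both drugs is in place by Day 22. That leaves 91 − 21 = 70 full-dose days. Completed before a draw on day d:

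- treated days = d − 1
- full-dose days = (d − 1) − 21

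| Chemistry draw | Day (window) | Treated days of 91 | Full-dose days of 70 |
|---|---|---|---|
| Visit 6 | 29 (27 to 31) | 28 (26 to 30) | 7 (5 to 9) |
| Visit 9 | 57 (54 to 60) | 56 (53 to 59) | 35 (32 to 38) |

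Take a participant who stops on Day 50 and has no later value. More than 28 days on drug is satisfied, and the cut-off is Day 50 + 3 = Day 53. The last scheduled draw inside it is Visit 6, because the Visit 9 window opens on Day 54. A value after about 7 full-dose days is then analysed as the result after 70. For a participant who stops on Day 80, the cut-off is Day 83 and the Visit 9 value is carried.

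Visits 6, 9 and 12 are all mandatory fasting visits (protocol 9.2 and 11.1), so the three triglyceride draws are comparable.

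**4. How many participants?** The only planning figure is 20% dropout: 0.20 × 50 = 10 per arm. On that figure, about 10 per arm is a ceiling on the number carried, since participants treated for 28 days or less are not imputed.

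**5. What does the protocol's model become with one post-baseline draw?** With a single post-baseline visit there is no visit term and no within-participant covariance. The MMRM reduces to a regression of change on treatment, gender and baseline among observed cases. That is the ANCOVA already in SAP 5.8.4.2, without the carried values.

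**The case against.** **For LDL and HDL, little changes in practice.** This stands. The stated ANCOVA is already the single-visit form of the protocol's analysis, and a rule that carries few values can distort little. The practical exposure is triglycerides.

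**A reader might infer that LDL and HDL have nothing at all to carry.** The documents do not support that. Protocol 8.3.1.2 asks participants who leave the trial to have end-of-treatment assessments promptly. SAP 5.1.4 and 5.1.6 allow unscheduled and early end-of-treatment lipid values. Such panels should be uncommon, because protocol 8.3.1.1 says: "Participants who discontinue trial product should continue with the scheduled visits and assessments to ensure continued counselling and data collection". But the LOCF limits do fit them.

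**A reader might infer that values from the titration phase are carried.** No scheduled value is. The first post-baseline chemistry draw is Day 29 (earliest Day 27), after maintenance is reached by Day 22. Only an unscheduled earlier sample, in someone treated for more than 28 days with no later draw, could be an exception.

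**A reader might compute an attenuation** as the share carried times the part of the effect not yet reached. The documents give no time course for lipids, so neither the size nor the direction follows. The formula also describes a mean difference, not a Hodges-Lehmann estimate.

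**A reader might extend the point to HbA1c**, where SAP 5.8.4.3 repeats the rule. That section is a descriptive count and percentage without a treatment comparison, and HbA1c is not among the protocol's legible exploratory endpoints. The MMRM argument does not carry over.

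**The triglyceride route is an inference.** Neither document says that the endpoint uses the Visit 6 and 9 chemistry values. It is the natural reading of the chemistry list with Table 2, and nothing in 5.8.4.2 excludes them.

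**Conclusion.** The point holds as a minor one. It is certain that SAP 5.8.4.2 departs from protocol 16.6.3 and that Section 8 does not declare it. It is also clear that carrying a value forward does not match a hypothetical estimand and treats imputed values as observed. For triglycerides, Day 29 or Day 57 values can stand as 13-week results, provided the chemistry-panel values feed the endpoint. For LDL and HDL the rule touches only occasional early or unscheduled panels.

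No bias figure is given because none can be derived. The endpoints are exploratory, and the primary weight analysis keeps its MMRM. The case for change is that the correction makes the analysis match the stated estimand at almost no cost.

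**What to change.** In the SAP:

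- Delete LOCF from 5.8.4.2.
- **LDL, HDL and total cholesterol:** run the stated ANCOVA (treatment, gender, own baseline) on observed on-treatment Week 13 values. State whether total cholesterol is drawn at Visits 6 and 9, since the chemistry list leaves this unclear.
- **Triglycerides:** use the protocol's MMRM on log values, with the on-treatment draws at Visits 6, 9 and 12 and the participant's own log baseline. The log scale addresses the skewness that led the SAP to a rank method. Keep Hodges-Lehmann and Wilcoxon on observed Week 13 values as supportive.
- **Section 8:** list and justify whatever still differs from protocol 16.6.3, including the log scale and the supportive rank analysis.

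The cost is SAP wording and one model statement, with no new data. The downside is that a few participants with only an early LDL or HDL panel no longer contribute a Week 13 value.

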#### 5.1.1 Data Summary

All summary tables will be presented by treatment group (K-757, K-757 + K-833, and placebo) and/or overall, as needed.

Unless otherwise specified, continuous variables will be summarized using descriptive statistics, the number of participants (n), mean, standard deviation (SD), minimum (min), first quartile (Q1), median, third quartile (Q3) and maximum (max). The min and max values will be presented to the same number of decimal places as the raw data. If the raw data has 3 decimal places or more, 3 decimal places will be presented for the mean and SD; 2 decimal places will be presented for medium, Q1, Q3, min and max. Otherwise the mean and median will be presented to one more decimal place than the raw data. The SD will be presented to two more decimal places than the raw data.

Summaries for categorical (discrete or dichotomous) variables will include the number and/or percentage of subjects in a particular category. Percentages will be presented to one decimal place, unless otherwise specified. Population counts (either number of subjects or number of time points at the assessment) for each treatment group will be used as the denominator in the calculation of percentages unless otherwise specified.

All tests of treatment effects will be conducted at a two-sided alpha level of 0.05 and/or two-sided 95% CI, unless otherwise stated.

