#### 6. Multiplicity

The study tests the primary hypothesis that at least one of the treatment arms is superior to the placebo arm in reducing the body weight calculated as percentage change from baseline after 13 weeks of treatment. Each of the two comparisons between K-757 alone and the combination of K-757+K-833 vs placebo is tested at two-sided alpha of 0.05 with a familywise error rate of 0.10. No other multiplicity adjustment will be performed for secondary and exploratory objectives, which will be tested at two-sided alpha of 0.05.

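### The triglyceride interval is 90% beside a two-sided 0.05 test, with no reason given, and triglycerides alone of the four lipids get no covariate adjustment.

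*SAP*

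**What the plan says.** SAP 5.8.4.2 covers change from baseline to Week 13 in four lipids. Total cholesterol, LDL and HDL are analysed by ANCOVA with "treatment, gender, baseline value as covariates". Triglycerides are treated separately, for one stated reason: "Triglycerides is not expected to be normally distributed". The Hodges-Lehmann method "will be used to estimate the median difference with 90% CI between treatment groups", and "A Wilcoxon rank sum test will be performed". No stratum or covariate is named for either.

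Three other places bear on this:

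- SAP section 6, on levels: "No other multiplicity adjustment will be performed for secondary and exploratory objectives, which will be tested at two-sided alpha of 0.05".
- SAP 5.1.1, on the default: "All tests of treatment effects will be conducted at a two-sided alpha level of 0.05 and/or two-sided 95% CI, unless otherwise stated".
- Protocol 16.6.3 gives exploratory endpoints the approach used for the secondary endpoint. For continuous endpoints (protocol 16.6.1 and 16.6.2) that is an MMRM with gender and, as written, baseline body weight. SAP section 8 declares no changes from the protocol.

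**The concern.** A 90% interval corresponds to a test at 0.10, and the test printed beside it is at 0.05. The two outputs for one comparison can therefore point in different directions, and nothing tells the reader which one governs. Non-normality is a reason for a rank or log method. It is not a reason for a different confidence level.

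The second issue is adjustment. Gender is the randomisation stratum and baseline triglycerides are collected at Day 1. Both gender and the baseline value are used for the other three lipids. Leaving them out for triglycerides gives up precision that the trial could have at almost no cost, and makes the four lipid results harder to read together.

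**Working it through.** **The plan's own figures.** The documents give no power, SD, effect or baseline correlation for triglycerides, so there is no triglyceride figure to reproduce. The primary-endpoint figure does reproduce: 50 x (1 - 0.20) = 40 per arm, difference 4, SD 4, two-sided 0.05 gives 99.3% to 99.4% power, consistent with the stated >95%. The familywise rate of 0.10 in SAP section 6 is 0.05 + 0.05 for the two primary comparisons. It does not explain a 90% triglyceride interval.

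**Interval against test.** The Hodges-Lehmann interval is the inversion of the Wilcoxon test. At a matching level the two agree, apart from ties and continuity correction. Here the levels differ:

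- A 90% interval excludes zero when |Z| > 1.645; the test is significant when |Z| > 1.960.
- They disagree when 1.645 < |Z| < 1.960, that is, when 0.05 <= p < 0.10.
- Under no effect the chance is 0.10 - 0.05 = 0.05 per comparison.
- With an effect, let theta = 1.960 + z(power). At 50% power theta = 1.960, and P(|Z| > 1.645) - P(|Z| > 1.960) = 0.624 - 0.500 = 0.124.

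| True power of the 0.05 test | Chance of disagreement |
|---|---|
| No effect | 5.0% |
| 30% | 11.8% |
| 50% | 12.4% |
| 80% | 7.6% |
| 90% | 4.5% |

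Width: 1.645/1.960 = 0.839, so the 90% interval is 16% narrower. Conversely, 1/0.839 = 1.19, so the 95% interval is about 19% wider.

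**Adjustment, by formula.** With equal variances and baseline correlation rho, unadjusted change has variance 2 x sigma^2 x (1 - rho) and ANCOVA has sigma^2 x (1 - rho^2). The ratio of ANCOVA to change is (1 + rho)/2. Under normality the Wilcoxon test has efficiency 0.955. If log-scale ANCOVA has 80% power (1.960 + 0.842 = 2.802), Wilcoxon on log change has power Phi(2.802 x sqrt(0.955 x (1 + rho)/2) - 1.960):

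- rho 0.5: 66%
- rho 0.7: 71%
- rho 0.8: 74%
- rho 0.9: 76%

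**Adjustment, by simulation.** All inputs are assumptions: lognormal triglycerides with median 130 mg/dL, a true 20% reduction, 40 per arm, and no gender effect. Figures are rounded and carry simulation error of about a point.

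| log-SD | rho | Wilcoxon, absolute change | Raw-scale ANCOVA | Log-scale ANCOVA |
|---|---|---|---|---|
| 0.4 | 0.8 | 93% | | 98% |
| 0.5 | 0.5 | 42% | 54% | 62% |
| 0.5 | 0.7 | 62% | 71% | 79% |
| 0.6 | 0.8 | 61% | 66% | |

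Over log-SD 0.4 to 0.6 and rho 0.5 to 0.8, the loss is about 5 to 22 points against log-scale ANCOVA and about 4 to 17 points against the raw-scale ANCOVA used for the other lipids.

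Part of the first gap comes from scale. At log-SD 0.5 and rho 0.7, Wilcoxon on log change reaches 69%, so about 7 of the 17 points come from taking logs. At log-SD 0.6 and rho 0.8 the scale share is about 10 of 17.

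**The case against.** The strongest defence is that the plan breaks no rule of its own. SAP 5.1.1 allows a different level where one is stated, and 5.8.4.2 states one. SAP section 6 governs the test, and the Wilcoxon test remains at 0.05. The rank test with a Hodges-Lehmann estimate is prespecified, valid under randomisation and robust to outliers, in a trial that admits triglycerides up to 600 mg/dL. The endpoint is exploratory and carries no power claim. All of this stands. What it does not supply is a reason for the 90% level or a way to read an interval and test that disagree.

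Four stronger readings are tempting and are not supported:

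- **That the error rate is inflated.** With a shared placebo arm and no effect, at least one of the two triglyceride intervals excludes zero about 17.6% of the time at 90%, against 9.1% at 95%. This matters only if a reader uses the 90% interval as the test. The Wilcoxon test's own rate stays at 5%.
- **That much power is lost.** The size depends on a correlation, SD and effect that the documents do not give, and lognormal data are the most favourable case for log-scale ANCOVA.
- **That baseline is ignored.** The section concerns change from baseline, so baseline is subtracted. What is missing is adjustment for it as a covariate.
- **That omitting gender costs power here.** No gender effect was simulated. Protocol 5.5 calls sex a covariate for weight response and does not extend that to triglycerides.

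Nor can it be said that every other interval is written as 95%. That level appears in the default and in the primary analysis; elsewhere it follows from the default.

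**Conclusion.** The mismatch is certain from the text: a 90% interval beside a two-sided 0.05 test, permitted by the exception clause but unexplained. The disagreement rate of 5% per comparison under no effect, and 4.5% to 12.4% at true power between 90% and 30%, needs no assumption about triglycerides beyond an approximately normal test statistic.

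The adjustment gap is also certain from the text, and the direction of its cost is consistent across the settings examined. The size, roughly 5 to 22 points against log-scale ANCOVA, holds only under the assumed inputs above and mixes adjustment with scale.

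SAP section 8 is incomplete on this point. The lipid methods in 5.8.4.2, including the ANCOVA for the other three, are not the approach in protocol 16.6.3, yet no change is declared. The severity is minor: no primary or secondary conclusion changes.

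**What to change.** - Report the triglyceride interval at 95%, matching the 0.05 test. If 90% is intended, state why and say that the test governs.
- Make the main triglyceride analysis an ANCOVA on log triglycerides with treatment, gender and log baseline, back-transformed to a percent difference from placebo.
- Keep the Hodges-Lehmann estimate and Wilcoxon test, at 95% and 0.05, as a supportive robust analysis.
- In SAP section 8, record that the lipid analyses depart from protocol 16.6.3, with the reason.

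The cost is SAP wording, one extra model and an interval about 19% wider. It should be settled before database lock, when the SAP is due to be final, so that neither the level nor the model is chosen after seeing data.
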